## Background

Cionic Inc., is a San Francisco based for-profit company specializing in developing a platform technology that enables hardware and software to enhance human mobility and improve overall quality of life. The Cionic-Apollo System is the first product under development, consisting of sensors that measures how muscles behave and how the body moves, and allows for targeted augmentation through electrical stimulation.

The purpose of this data collection study is to capture information about how the body moves using the Apollo System's sensor system in order to build algorithms for providing targeted external electrical muscle stimulation to individuals with impacted mobility. In addition, Cionic will use this data collection study as an opportunity to further inform design changes and reinforce safety and efficacy of the product.

Cionic is preparing for a 510(k) submission of it's Apollo System, and while there is no requirement from the FDA for any testing on human participants, Cionic recognizes the need to conduct this data collection on both adult and pediatric impacted populations.

## Organizational Relationships

Cionic is working closely with Edge Analytics, a consulting firm who has been contracting for Cionic for over a year. They are primarily responsible for algorithm development, and are working closely on this data collection study. [name] is a cofounder of Edge Analytics and a sub-investigator on this study.

Starfish Therapies is a physical therapy clinic in Burlingame, CA owned by [name] where pediatric data collection will take place. Starfish is not being compensated in any way to allow Cionic to use their clinic as a data collection site. The data collection process and study administrators will be identical for all sessions completed at Starfish

## Specific Aims

This protocol describes a data collection study intended to inform the development and refinement of the Apollo system. This device has been designed to collect raw movement data from the participant, convert this data into clinically relevant measures such as limb orientation and muscle activation, and to deliver functional electrical stimulation (FES) to support and augment muscle activation in order to account for movement deficits. The study consists of three independent data collection Sessions (Table 1), each accomplishing one of the Study Aims.

### AIM 1 - Movement measurement

Session A of the study is designed to collect physiological data on impacted participant populations in order to record and characterize movement from people with lower body deficits. This will be accomplished by recording kinematic data (movement velocity, range of motion) and functional data (muscle activation signals via electromyography (EMG). The output of this session will be data recorded from the system which is de-identified and used for internal Cionic engineering and software development. This Session does not involve electrical stimulation.

### AIM 2 - Muscle Activation and Usability

The Apollo System consists of a wearable leg strap with sensors, designed for accurate, repeatable, and comfortable use by participants irrespective of movement deficits. The leg strap includes an array of adhesive stimulation electrodes that must be positioned accurately over target nerves and muscles. Session B of the study will test different electrode placements on the leg to determine which positions result in the optimal muscle activation. This session will also evaluate the comfort of stimulation using these electrodes during extended use as a measure of usability.

### AIM 3 - FES for Gait Assistance

Session C is to characterize and collect data on the impact of electrical stimulation on impacted participants' gait. This study involves placement of electrodes onto participants and delivering patterns of stimulation optimized to allow the participant to have an improved gait, as characterized by increased range of movement, speed, and self-reported assessment of their assisted walking.

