### Task 3: Treadmill trial

- Participant will be guided onto a treadmill with side handles.
- An overhead safety harness will be fitted to the participant.
- Walking will be initiated on the treadmill at a rate no more than the participant's comfort level at a participant-reported speed for up to 5 minutes while movement data is collected.

Data will be reviewed to confirm readiness for treadmill gait protocol.

- The process will then be repeated up to 5 times for walking intervals of up to 2 minutes while data is collected and reviewed.
- Verbal check-in with participant for pain, understanding and need for a break.

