## Task 4: Treadmill trial with stimulation assist

- Participant remains on the treadmill with side handles.
- An overhead safety harness remains fitted to the participant.
- A gait assist algorithm will be entered into the Apollo system.
- Walking will be initiated on the treadmill at a rate no more than the participant's comfort level
- After notifying participant, the electrical stimulation algorithm will be applied to the leg electrodes, starting at 0mA and slowly increased until effective gait is achieved or the participant reports discomfort. If pain or discomfort is reported the stimulation and treadmill will be stopped immediately.
- The process may be repeated up to 10 times with different gait assist algorithms.
- Verbal check-in with participant for pain, understanding and need for a break.

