## Risk Mitigation Strategies

Cionic has done the following things to reduce the risks to participants.

- Have done internal experiments and made design modifications to increase safety
- Cionic team is well trained and to strictly follow the study protocols
- Participants will have the option to wear a safety harness secured overhead to protect them from falls. Session C will require all participants to be in harness.
- The testing area will be safe, well lit and clear of all obstacles
- Any actions will be discussed with the participant prior and their comfort will be monitored throughout the study
- Participants will self manage a walking speed and control their level of electrical stimulation for their own comfort level
- A COVID safety protocol will be strictly adhered to, requiring all people who visit the site to check temperatures, practice social distancing, require mask

wearing and follow all other CDC guidelines to prevent the spread of COVID-19

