#### Statistical Analysis

This is a broad study intended to collect data on individual participants. Key measurements such as walking speed, range of motion and muscle activation may be pooled for determination of average values and deviation. This study is not intended to generate statistically significant data intended to infer any clinical diagnosis or recommendation.

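### Aim 3 counts increased speed as a benefit of FES, but Session C has no rule that matches, re-selects or records treadmill speed with stimulation off and on

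*Protocol*

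**What the plan says.** Aim 3 (Protocol, AIM 3 - FES for Gait Assistance) assigns Session C to show how stimulation affects gait, with improvement "characterized by increased range of movement, speed, and self-reported assessment of their assisted walking". Speed is one of three named components.

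Session C contains two walking tasks, both on a treadmill:

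- Task 3, without stimulation: "Walking will be initiated on the treadmill at a rate no more than the participant's comfort level at a participant-reported speed". The first bout lasts at most 5 minutes, and as many as five shorter ones follow, each of 2 minutes or less.
- Task 4, with stimulation: "Walking will be initiated on the treadmill at a rate no more than the participant's comfort level". The next step is that "the electrical stimulation algorithm will be applied to the leg electrodes, starting at 0mA and slowly increased until effective gait is achieved". Reported discomfort also ends the increase.

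Task 5 is exercise, not walking. The protocol's only overground walk is Session A Task 4, and Session A has no stimulation.

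The Risk Mitigation Strategies section adds: "Participants will self manage a walking speed and control their level of electrical stimulation for their own comfort level". The protocol's Statistical Analysis section says: "Key measurements such as walking speed, range of motion and muscle activation may be pooled". It ties none of these to a session.

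The SAP compares FES with noFES in pairs, averages each metric over a participant's steps, and corrects for four outcome metrics at 0.0125. It does not name the four.

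**The concern.** On a treadmill, mean walking speed over a bout is the belt speed. It responds to FES only if someone changes the belt, and the protocol does not say who changes it, when, or by what procedure once stimulation is on. One of Aim 3's three components therefore has no written measurement procedure in the session meant to answer it.

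The problem is not confined to speed. Range of motion and other step-level measures can be expected to vary with walking speed. If the belt runs at one rate in Task 3 and another in Task 4, a paired difference in those metrics mixes the effect of stimulation with the effect of speed. Nothing in Session C or the SAP prevents this, and without recorded belt speeds it could not be detected afterwards.

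**Working it through.** **Step 1. The two conditions side by side.**

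| | Task 3 (noFES) | Task 4 (FES) |
|---|---|---|
| Surface | Treadmill | Same treadmill |
| Rate | Participant-reported, capped at comfort | Capped at comfort |
| Order | First | Second |
| Start of walking | No stimulation | Listed before stimulation is raised from 0 mA |
| Rule matching speed to the other condition | None | None |
| Rule re-selecting speed under FES | Not applicable | None |
| Belt speed recorded as a result | Not stated | Not stated |

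**Step 2. What the speed difference can be.** Write D = (mean speed with FES) - (mean speed without FES). On a belt, D = (belt setting in Task 4) - (belt setting in Task 3).

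- Belt unchanged: D = 0 for every participant, whatever FES does.
- Belt changed: D is the size of that change. It is made by a participant who has been told stimulation is starting, under no script, and always in the second condition. By then the participant may have walked up to 5 + 5 x 2 = 15 minutes on the treadmill in Task 3. Practice, fatigue and expectation act in the same comparison as the device.

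Neither value of D can be attributed to FES.

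**Step 3. The SAP's own sample size.** Inputs from the SAP's Power Analysis: effect size d = 0.7, alpha 0.05, 80% power, 18 participants. Sidedness is not stated; I assume two-sided. For a paired t-test, power = P(|T| > t(1 - alpha/2, n - 1)), where T is noncentral t with n - 1 degrees of freedom and noncentrality d x sqrt(n).

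At n = 18, the noncentrality is 0.7 x sqrt(18) = 2.970 and the critical value is 2.110, so power is 79.9%. The stated figure is reproduced to rounding. (Strictly, 19 participants are needed to reach 80%, with power 82.3%.)

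**Step 4. The Bonferroni consequence, only if speed is one of the four metrics.** Removing it leaves three, so alpha = 0.05/3 = 0.0167 instead of 0.05/4 = 0.0125. I use n = 18 (SAP) and n = 20 (Session C in Table 1: about 10 adults + 10 children).

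| n | Power at 0.0125 | Power at 0.0167 |
|---|---|---|
| 18 | 57.9% | 62.7% |
| 20 | 64.6% | 69.1% |

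The gain is 62.7 - 57.9 = 4.8 points, or 69.1 - 64.6 = 4.5 points, for each remaining metric with a true effect of 0.7.

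**Step 5. Why matching must be planned and not done afterwards.** Suppose bouts were kept only where speeds happened to agree, and two participants were lost. From n = 20 at 0.0125 (64.6%), n = 18 at 0.0167 gives 62.7%. From n = 18 at 0.0125 (57.9%), n = 16 at 0.0167 gives 55.5%. Either way the gain in Step 4 is gone. Such filtering also selects on a variable that FES may itself have changed.

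**The case against.** The strongest reply is that the rate is not imposed. Task 3 makes it participant-reported, and Risk Mitigation Strategies has participants manage their own walking speed. A comfortable speed freely chosen with FES on and off is information, and it could be compared in pairs. This stands as far as it goes. A reader might infer that Session C fixes the belt and so makes speed untestable in principle. The documents do not support that: they neither fix the rate nor require it to be equal. What is missing is a rule to choose and record it in each condition.

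Second, no planned test of speed is shown. A reader might infer that speed occupies one of the SAP's four places and uses up a quarter of the error rate. The SAP names no metric, so this is neither shown nor excluded, and the power figures in Step 4 are conditional. The protocol's Statistical Analysis section does not settle it: it mentions pooling without reference to Session C, and Session A's overground walk could supply walking speed. The mismatch with Aim 3 does not depend on this point.

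Third, speed in Aim 3 might mean limb velocity, since Aim 1 lists movement velocity among its kinematic data and the worn sensors could measure it. That reading is possible but strained in a sentence about improved gait and assisted walking. If it is what the sponsor meant, Aim 3 should say so. The confounding of other gait metrics by belt speed would remain.

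**Conclusion.** The concern holds in this form: Aim 3 names speed as a mark of benefit, and Session C provides no procedure that makes walking speed a measured response and not a treadmill setting. Followed as written, the speed contrast is either zero by construction or an unscripted, order-confounded choice. Unequal belt speeds can also bias the other paired gait metrics. How large that bias would be cannot be given, because the documents report neither belt speeds nor the dependence of any metric on speed.

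This should be corrected before the Session C comparison is relied on. The conclusion rests on the written tasks being the full procedure, on speed in Aim 3 meaning walking speed, and on gait metrics varying with speed. The power change of about 5 points applies only if speed is among the four metrics, and assumes a two-sided paired t-test at effect size 0.7.

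**What to change.** 1. In Session C Tasks 3 and 4, record belt speed for every bout.
2. State in advance that the noFES and FES bouts entering the paired comparison are run at the same belt speed, one that the participant finds comfortable in both conditions. Make this an instruction for running the bouts, not a filter applied to the data later.
3. Remove walking speed from the Session C benefit measures in Aim 3, and do not use it as one of the SAP's tested metrics, unless it is re-selected by the same scripted procedure in each condition or measured in a self-paced overground walk with FES off and on. The walk in Session A Task 4 is a ready template. Adding either is optional.
4. Name the four metrics in the SAP. Change the divisor from four to three only if speed proves to be one of them; otherwise 0.0125 stays.

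The cost is a line in Aim 3, a few lines in Tasks 3 and 4 and the SAP, one extra recorded value per bout, and slightly more control over how bouts are set up. The treadmill bouts would then support no claim about speed.

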**Table 1. Summary of protocol session**

	Session A	Session B	Session C
Specific Aim	Movement measurement	Muscle activation & usability	FES for Gait Assistance
Involves data collection?	Yes	Yes	Yes
Involves stimulation?	No	Yes	Yes
Approximate # of adult participants	20	20	10
Approximate # of pediatric participants	10	10	10
Activity	Measure movement during walking without any intervention.	Measure muscle activity and effect of FES on muscles only (no movement).	Measure effect of FES on gait.

## **Participant Selection**

This data collection study is looking to recruit up to a total of 50 different adult participants and 30 different pediatric participants. There are three independent sessions in the study, with a decreased number of participants needed for Session C (Figure 1). There are no gender-based or ethnicity restrictions. Adult participants between the age of 18-70 and pediatric participants may be between the ages of 6-17.

### Inclusion criteria

[figure not shown]
- Are living with lower extremity impairment that makes walking difficult and/or uncomfortable
- Capable of sitting, standing and walking with or without assistance
- Ability to walk at least 10 meters with minimal assistance

[figure not shown]
- Ability to understand and follow the basic instructions in English
- Parent/guardian must be accompany and be present with pediatric participants

### Exclusion criteria

- Having non-reversal damage to the central and peripheral body's system
- Underlying pre-existing conditions like thrombosis/hemorrhage, severe epilepsy or other seizure disorder, severe atrophy or history of implanted electrical devices
- Cognitive impairment that would prevent the participant from fully understanding the study and ability to provide informed consent
- Lower motor neuron disease or injury that may impair response to stimulation
- Pregnant woman
- Skin conditions of the affected lower limb, including cuts, burns or lesions
- Latex allergy

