**Figure 1. Participant distribution by Session**

## Methods

The Cionic wearable devices measure information about leg and muscle activity that enable mobility. The system consists of four leg straps, two foot sensors, and two foot insoles (or pressure array of pressure sensors), connected by insulated wires to a battery-powered control box worn on the thigh. The device can also be (optionally) configured to attach sticky electrode pads to the body, which are connected to an integrated battery powered control box worn at the hip, capable of stimulating muscle contractions.

The Cionic sensing devices are made up of sensors that are either part of compression-type wearable garments held snugly in place with velcro and sticky electrode gel, or attached to the shoes. This system will measure what the body, i.e., pelvis and legs, are doing while the participant. It also has sensors that measure what some of the body's muscles are doing during movement. When muscles are working,

they produce a small electric current that can be measured with sensors on the skin over the muscle.

Each participant will be asked to wear:

- Two elastic leg straps (Figure 2), containing multiple sensors, will be secured to each leg with Velcro. One strap will be secured around each thigh and one around each shank (lower leg). These straps will measure two things: (1) the activity levels of the muscles underneath the straps, and (2) the physical orientation of the legs.
- One foot sensor will also attach to the top of the participant's shoes to measure the physical orientation of the feet. The straps and foot sensors will be connected by stretchable wires.
- Lastly, thin pressure-sensing pressure pads (Figure 3) will be inserted inside each of the shoes. The pressure sensors measure where the foot is applying downward pressure inside the shoes at all times.

Participants in sessions B and C will wear the Cionic stimulation device (Figure 4), which includes all of the above, as well as sticky electrode pads connected to a battery powered control box worn at the hip, capable of stimulating muscle contractions (manually or algorithmically).

- One Functional Electrical Stimulation (FES) control box clipped to the hip.
- Maximum of eight pairs (16 total) sticky electrode pads worn at one time on the shins, calves, quadriceps, and/or hamstrings. These electrodes will connect to the FES control box via insulated wires.

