### **Session A - Sensor Data Collection**

Session A will consist of approximately 2 hours of sensor data collection. The participant will be outfitted with a Cionic leg straps on the thigh and shank of both legs and foot pressure sensors taped under both shoes. The leg straps consist of EMG (non-invasive muscle electrical signals) sensors and IMU (accelerometry/movement signals) sensors. Participants will be asked to wear clothing amenable to sensor placement and movement such as shorts.

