## Risk & Benefit Assessment

The Apollo System represents minimal risk to the participants participating in each session of the data collection study. Like with any study of this kind, there are some known risks, that although rare, are associated with participation:

- Some participants may experience slight pain or discomfort from the electrical stimulation
- Minor skin irritation at the site of sensor/electrode placement
- Some participants may experience anxiety or anxiousness due to the anticipation of receiving an electrical stimulation
- Injury caused by unintended falls
- Exposure to COVID-19 or other communicable disease

It is not always possible to know all of the risks associated with a study like this one. If any new risks are reported for this study, someone from the study team will let the participant know so that they can decide if they would like to continue taking part.

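### The skin exclusion covers only the affected leg, but sensor straps go on both legs, so skin damage on the other leg is not a written reason to exclude

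*Protocol*

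**What the plan says.** The skin criterion in the protocol's Exclusion criteria reads "Skin conditions of the affected lower limb, including cuts, burns or lesions". It is in the singular and tied to the affected limb, a term that the protocol does not define. The legible part of the Inclusion criteria asks that candidates "Are living with lower extremity impairment that makes walking difficult and/or uncomfortable". It does not say whether one leg or both must be impaired.

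Device placement is described without regard to the affected side. Under Methods, "Two elastic leg straps (Figure 2), containing multiple sensors, will be secured to each leg with Velcro", one at the thigh and one at the shank. The Session A section places the "leg straps on the thigh and shank of both legs". Methods also states that the sensing garments are kept in place by Velcro and an adhesive gel, and that participants in Sessions B and C wear all the sensing equipment plus stimulation pads. The pad limit is given as "Maximum of eight pairs (16 total) sticky electrode pads worn at one time on the shins, calves, quadriceps, and/or hamstrings", with no mention of side.

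The Risk & Benefit Assessment lists "Minor skin irritation at the site of sensor/electrode placement", again without limiting it to one leg.

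**The concern.** The criterion's evident purpose is to keep the device off damaged skin. It does that only if the skin it screens is the skin the device touches. For someone with one-sided weakness the two differ: the rule looks at one leg and the equipment goes on two. A candidate with a healing burn on the stronger leg meets no written reason for exclusion, although the fitting instructions call for straps on that leg as well.

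What is at stake is participant safety and consistent application of eligibility, in a study that plans up to 50 adults and 30 children. Staff who find such a lesion at setup have no written rule to follow, so different staff could handle the same case differently.

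**Working it through.** The plan states no figure on this point. The check sets the sections side by side and counts sites.

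**1. Where the straps go.** From Methods: 2 straps per leg × 2 legs = 4 strap sites. Session A confirms both legs. Sessions B and C inherit the same equipment through Methods.

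**2. What the criterion covers.**

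| Impairment | Limbs that count as affected | Strap sites covered by the skin criterion |
|---|---|---|
| Both legs | 2 | 2 × 2 = 4 of 4 |
| One leg | 1 | 2 × 1 = 2 of 4 |

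The gap exists only in the second row. The legible inclusion text admits people in either row.

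**3. Whether pads add to the gap.** The four muscle groups are tibialis anterior, quadriceps, gastrocnemius and hamstrings (Session B, Task 4). Two layouts reach the stated maximum:
- 4 groups × 2 legs × 1 pair = 8 pairs = 16 pads
- 4 groups × 1 leg × 2 pairs = 8 pairs = 16 pads

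The maximum therefore does not tell one-legged from two-legged stimulation. Session B also describes testing several pad locations per muscle and applying an array of electrodes to one muscle group, which fits the second layout. Aim 2 describes stimulation electrodes as part of the leg strap, which leans the other way. No section settles it.

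**4. Whether anything else closes the gap.**
- The other exclusion criteria do not mention the skin. Latex allergy is a separate matter.
- The video screening in the recruitment Method concerns safe walking and comprehension.
- The anatomical measurement and equipment setup tasks in all three sessions cover limb measurements, strap comfort, device connection and calibration. None includes looking at the skin.
- Risk Mitigation Strategies covers design changes, training, the harness, the testing area, comfort, participant control of speed and stimulation, and COVID precautions. It does not cover skin condition.
- No section confines straps or pads to the affected leg.

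**The case against.** The strongest reply is that the gap is narrow and that practice would probably close it. *Affected* is undefined. If both legs are impaired, both are covered, and the documents do not say how many participants are impaired on one side only. Part of the inclusion list is a figure that is not shown. For harm to occur, one-sided impairment, a lesion on the other leg and a strap or pad over that lesion must coincide. Straps are fitted in person on participants asked to wear clothing such as shorts, comfort is confirmed at setup and monitored throughout, and stimulation starts at zero and is stopped on discomfort. The harm listed is minor skin irritation.

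Much of this stands. It limits how often the gap matters and makes unnoticed placement on broken skin less likely. It does not remove the mismatch, because comfort checks are not skin checks and no section tells staff what to do if they see a lesion.

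A reader might infer more than the documents support:
- **That the protocol directs the device onto broken skin.** Not being excluded is not the same as being fitted over a lesion. Staff could decline at setup, although nothing requires them to.
- **That up to four of the eight pad pairs are on unscreened skin.** This assumes an even split between legs, which is stated nowhere.
- **That half the contact area, or half the risk, is missed.** Two of four is a count of strap sites. It measures neither area nor risk.
- **That the screener survey repeats the gap.** Its content is not in the documents, and it may already ask about both legs.

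**Conclusion.** The point holds as a mismatch between a stated eligibility rule and the protocol's own device placement. For a participant with one-sided impairment, the criterion covers two of the four strap sites, and no other section covers the remaining two. For a participant with both legs affected there is no gap.

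This rests on reading *affected* as the impaired limb, its ordinary sense next to an inclusion criterion about impairment, and on the legible part of the inclusion list. The firm part concerns the sensor straps, which are explicitly on both legs. Stimulation pads on the unaffected leg are permitted but not stated, so they should not be counted in the size of the problem. The number of people concerned is unknown. This is an eligibility and safety clarification that is worth making and easy to make. It has no bearing on the SAP's power analysis or tests.

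**What to change.** The sponsor should reconcile the skin criterion in Exclusion criteria with the placement text in Methods and Session A. The revised criterion should keep all its present coverage of the affected limb and extend to the other leg wherever the device is worn. Wording such as *of either lower limb* would do this. A version limited to strap and pad sites would be worse in one respect. Read literally, it would drop lesions elsewhere on the affected limb that the current text covers.

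The screener survey should be checked against the revised criterion. It would also help to state whether stimulation pads may be placed on the unaffected leg.

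The cost is one phrase in the exclusion list and, if needed, a matching item in the screener. The downside is that a few candidates with lesions on the unaffected leg may be deferred or excluded. The documents give no basis for estimating how many.

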#### Task 4: Isolated muscle group data collection

- An array of 2" x 2" adhesive electrodes (typical of TENS therapy system) will be applied to a muscle group of interest.
- Sensors will be calibrated by guiding the participant through specific limb movements both standing and sitting.
- Participants will be asked to move their feet and legs to access their range of motion
- Stimulation will be delivered to different combinations of electrodes on the muscle group. At each instance stimulation will be started at the lowest setting (0mA) and increased slowly until either a sufficient muscle response is achieved or the participant reports discomfort. If any discomfort is felt, stimulation will be immediately stopped, and a new combination of electrodes will be selected.
- Verbal check-in with participant for pain, understanding and need for a break.

Muscle Group	Tibialis Anterior	Quadriceps	Gastrocnemius	Hamstrings
Participant position	Supine	Seated	Prone	Prone
Intended Movement	Foot dorsiflexion	Lower leg extension	Foot plantar flexion	Lower leg flexion

After completion of all tasks, equipment will be removed from the participant and sanitized with isopropyl alcohol. A brief post-study survey will be administered verbally or via computer by the study coordinator.

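### The exclusion criteria cover latex allergy but not a known allergy or skin reaction to the electrode gel and adhesive pads that the protocol describes on the skin

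*Protocol*

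**What the plan says.** Two items in the protocol's Exclusion criteria bear on skin or allergy. One is "Latex allergy". The other is "Skin conditions of the affected lower limb, including cuts, burns or lesions".

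Methods describes what touches the skin. The sensing devices are partly "compression-type wearable garments held snugly in place with velcro and sticky electrode gel". The list of worn items opens with "Each participant will be asked to wear" and puts a strap on each thigh and each shank, so both legs are covered. Methods then adds: "Participants in sessions B and C will wear the Cionic stimulation device". That device brings a "Maximum of eight pairs (16 total) sticky electrode pads worn at one time on the shins, calves, quadriceps, and/or hamstrings". Session B, Task 4 confirms the material: an array of "adhesive electrodes (typical of TENS therapy system) will be applied to a muscle group of interest".

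The Risk & Benefit Assessment names "Minor skin irritation at the site of sensor/electrode placement" among the known risks, which it calls rare. Risk Mitigation Strategies lists internal testing and design changes, staff training, the harness, a clear testing area, discussion and monitoring of comfort, participant control of speed and stimulation, and COVID precautions. No item is directed at skin reactions.

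The recruitment section describes a short screener survey, whose questions are not given, and a video call that checks safe walking and comprehension.

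**The concern.** An allergy exclusion is there to keep out people who are likely to react to something the study puts on them. Here the only allergy named is latex, while the skin-contact materials the protocol itself describes are gel and adhesive. The protocol also recognises irritation at the contact sites as a hazard. Someone who already knows that they react to these materials is the easiest person to identify before enrolment, and the written criteria give the study team no ground to exclude them.

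What is at stake is participant safety at a minor level, in a study that plans for about 30 children as well as adults. No analysis result depends on it.

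**Working it through.** The plan gives no figure to reproduce on this point, so the check is a comparison of sections.

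1. **Materials on the skin, by session.** Session A involves no stimulation, so it uses no stimulation pads. Its exposure is to the gel of the sensing garments. Sessions B and C have the same garments plus adhesive pads, up to 16 at one time.

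2. **Number exposed by design (Table 1 in the protocol).**
   - Session A: 20 adults + 10 children = 30
   - Session B: 20 + 10 = 30
   - Session C: 10 + 10 = 20
   - Garments, all sessions: 30 + 30 + 20 = 80
   - Adhesive pads, Sessions B and C: 30 + 20 = 50

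   Table 1 calls these counts approximate. Participant Selection gives 50 adults and 30 children as upper limits, so 80 is a ceiling.

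3. **Does the allergy item cover gel or adhesive?** No. It names latex only.

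4. **Does the skin item cover them?** Its wording is open, so the three examples do not limit it, and an active rash on the affected limb would fall under it. A history of reaction with intact skin is not a present condition of that limb. Latex allergy is listed separately, which suggests that allergy was not meant to be read into the skin item. The item also concerns the affected limb, whereas straps go on both legs.

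5. **Does anything else in the protocol catch it?** The screening call, as described, covers walking and comprehension, and the section on capacity covers decision-making and language. The remaining exclusions concern neurological and other medical conditions, cognition and pregnancy. The figures missing from the text fall in the inclusion list; the exclusion list shows no sign of a gap.

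6. **Result.** A person with intact skin and a known reaction to gel or adhesive meets no listed exclusion, in any session.

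**The case against.** The strongest reply is that this is an optional change of wording. The protocol already discloses the risk, calls it minor and counts it among rare ones. Staff confirm strap comfort at setup and check in verbally during tasks, participants may withdraw at any time, and the investigator reviews adverse events within one business day. All of that stands, and it keeps the point small. These measures act once the material is on the skin, however, whereas an eligibility criterion acts before.

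The reply is also right on exposure. Adhesive pads are confined to Sessions B and C, and 16 is a maximum. The two hours given for a session is its length, not the time a pad is worn, and the pediatric accommodations aim for under 1.5 hours. For Session A, contact with gel rests on one general sentence in Methods; the list of worn items mentions only Velcro.

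Several stronger readings are tempting, and the documents do not support them:

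- *That the sponsor knowingly admits people with this allergy.* The criteria are silent, which does not show a decision.
- *That screening never asks.* The content of the survey and of the call script is not shown, so the question may already be there. Even so, the written criteria would not exclude on the answer.
- *That a skin reaction would distort the discomfort reports that limit stimulation.* In Session B and in the Session C treadmill task, discomfort is one of two end points for raising the current; the other is an adequate muscle response or effective gait. Nothing says that a reaction would appear during the session or be mistaken for stimulation discomfort.
- *That the latex item is misplaced.* The composition of the elastic straps and stretchable wires is not stated, so the documents do not show that it is unneeded.

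**Conclusion.** The point holds as a gap in eligibility wording: the exclusions leave out known allergy or skin reaction to the gel and adhesive that the protocol describes on the skin, although irritation at those sites is a named risk with no specific mitigation. It rests on the exclusion list being complete as shown and on the Methods sentence about gel applying to all sessions. If gel were not used in Session A, the point would still hold for the roughly 50 participants in Sessions B and C.

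The expected harm is minor. The SAP's sample size, significance level and paired comparison are unaffected.

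The documents give no frequency of such sensitivity. Purely as an assumption, if 1% to 5% of 80 participants had a known sensitivity, the expected number would be 80 × 0.01 = 0.8 to 80 × 0.05 = 4, and the chance of at least one would be 1 − 0.99^80 = 55.2% to 1 − 0.95^80 = 98.3%. These figures count sensitive people, not reactions, and use the enrolment ceiling. The conclusion does not depend on them.

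**What to change.** In the protocol's Exclusion criteria, extend the latex item to read: *Latex allergy, or known allergy or skin reaction to medical adhesives or electrode gel.* Check the screener survey described in the recruitment section, and add a matching question if it has none.

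The cost is one phrase and at most one question. The downside is the possible loss of a few candidates. The SAP needs no change.
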